17.6 Analysis of secondary endpoints

17.6.1 *Pharmacokinetics*

Refer to section 17.5.1.

17.6.2 *In vivo extracted amount of nicotine*

The data needed for the analysis of in vivo extracted amount of nicotine are the individual data of amount of nicotine for unused reference pouches and the amount of nicotine left in the study pouches. The mean nicotine concentration of the reference pouch and weight of each individual study pouch and residual nicotine amount will be used to calculate the extracted amount. The mean of extracted amount (mg/unit) and extraction fraction (%) of nicotine for each IP pouch, will be calculated. The extracted dose of nicotine will be analysed using the signed Wilcoxon rank sum test for within subject difference (i.e. between IPs). Amount of

nicotine in reference pouches and in used pouches will be presented through descriptive statistics.

17.6.3 *Products evaluation scale*

Each sub-question, sub-category and the total score of Questions 1a-g (sub-category 1), 2a-j (sub-category 2), 3a-y (sub-category 3) and 4a will be presented using descriptive statistics at selected timepoints by product including a graph of the mean at each time point.

The total score of PES and the sub-categories will be calculated for each product and intraindividual difference for each timepoint assessed will be analysed using a Wilcoxon Signed Rank Sum test.

17.6.4 *Modified cigarette evaluation questionnaire*

Frequency (number and percentage) for each sub-question will be presented using tables.

17.6.5 *Products preference scale*

The sub-questions 1 will be presented using a frequency table with number of observations and all combinations of the subject's preference.

The sub-question 2 will be presented using a frequency table with number of observations and percent.

No statistical testing will be performed on sub-questions.

17.6.6 *Adverse events*

An overview of all AEs, including SAEs, intensity, relationship to IP, and deaths will be presented by SOC and PT.

Incidence of AEs and SAEs will be summarised by SOC and PT by sequence and overall.

All AE data will be listed by subject and include the verbatim term entered by the Investigator.

17.6.7 *Clinical laboratory analyses*

Clinical laboratory data will be summarised overall with absolute and percent change from baseline.

Abnormal, clinically significant values will be summarised separately, if considered appropriate.

All data will be listed by subject.

17.6.8 *Vital signs*

Vital signs (systolic/diastolic blood pressure and pulse) will be summarised by sequence. Data will be presented with absolute and percent change from baseline.

All data will be listed by subject.

17.6.9 **12-lead ECG**

All ECGs will be categorised as "normal", "abnormal, not clinically significant", or "abnormal, clinically significant" (as judged by the Investigator) and summarised by sequence using frequency tables.

Changes over time will be presented using shift tables, if considered appropriate.

All data will be listed by subject.

17.6.10 **Total exposure (cotinine in plasma)**

The analysis and presentation of total nicotine exposure following plasma cotinine levels (concentration, applicable calculated PK parameters and number of *ad lib* IP units used) following controlled single use and *ad lib* use of IP will be further specified in the SAP.

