9.3 Number of subjects

Twenty Four subjects will be included in the study. Approximately 48 subjects will be screened to achieve a total of 24 randomised subjects.

For replacements of subjects who discontinue from the study, see Section 9.8.

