10.1 Identity of investigational products

A: ZoneX #2, OND, white tobacco-free nicotine pouch, 5.8 mg nicotine/pouch
B: ZoneX #3, OND, white tobacco-free nicotine pouch, 10.1 mg nicotine/pouch

Comparators:

C: Skruf snus fresh slim white, 10.9 mg nicotine/pouch
D: [REDACTED]
E: Marlboro Gold, conventional cigarette, 0.8 mg nicotine/cigarette

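### The signed-rank test on extracted nicotine dose leaves out the sampling error of the mean reference-pouch concentration that all subjects share, so its p-values can be too small, chiefly for products of similar content

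*Protocol*

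**What the plan says.** Protocol section 17.6.2 names as inputs "the individual data of amount of nicotine for unused reference pouches" and the nicotine left in each used pouch. For the calculation itself, "The mean nicotine concentration of the reference pouch and weight of each individual study pouch and residual nicotine amount will be used". So, for each subject and pouch product, extracted amount = mean reference concentration of the product × weight of the subject's own pouch − residual nicotine.

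The comparison of products is also fixed: "The extracted dose of nicotine will be analysed using the signed Wilcoxon rank sum test for within subject difference (i.e. between IPs"). Beyond supplying the mean, the reference pouches are only described: "nicotine in reference pouches and in used pouches will be presented through descriptive statistics".

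On numbers, section 9.3 says "Twenty Four subjects will be included in the study", and section 10.1 lists "A: ZoneX #2, OND, white tobacco-free nicotine pouch, 5.8 mg nicotine/pouch", "B: ZoneX #3, OND, white tobacco-free nicotine pouch, 10.1 mg nicotine/pouch" and "C: Skruf snus fresh slim white, 10.9 mg nicotine/pouch". The content of D is redacted. Extracted dose is a secondary endpoint (section 7.2).

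**The concern.** The mean reference concentration is an estimate from a sample of unused pouches. If it is 2% too high for product B, every subject's extracted dose of B is too high by 2% of that pouch's calculated content. In B versus C, all subjects' differences then move in the same direction by nearly the same amount.

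A signed-rank test judges a shift only against the spread of the differences across subjects. A shift common to all subjects adds almost nothing to that spread, so the test cannot tell it from a product effect. Weighing each pouch does not help, because the same uncertain concentration multiplies every weight. Recruiting more subjects does not shrink the shared error either; only more reference pouches do.

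At stake is a false statement that two products release different amounts of nicotine. It matters most where true extraction may be close. B versus C is such a pair, since section 8.2 says the snus comparator was chosen for a nicotine strength like that of the investigational product.

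**Working it through.** The protocol gives no figure to reproduce here: no number or spread of reference pouches, no SD of differences, and no significance level for this test.

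**Inputs from the protocol:** 24 pairs (section 9.3); contents 10.1 mg (B), 10.9 mg (C) and 5.8 mg (A) (section 10.1).

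**Assumptions:** pouch-to-pouch CV of nicotine concentration 1-5%; k = 5 to 50 reference pouches per product; SD of within-subject differences 0.9-2.0 mg; two-sided 5% test; independent reference errors for the two products; no true difference.

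**Formulas**

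- Shared SE of the B−C difference = CV/√k × √(10.1² + 10.9²) = CV/√k × 14.86 mg
- SE that the test sees = SD/√24
- r = shared SE / test SE
- Approximate true type I error = 2 × [1 − Φ(1.96/√(1 + r²))]

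**Example** (CV 3%, k = 5, SD 0.9 mg): shared SE = 0.03/√5 × 14.86 = 0.199 mg; test SE = 0.9/√24 = 0.184 mg; r = 1.085; 1.96/√(1 + 1.085²) = 1.328; type I error = 18.4%.

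**True type I error of a nominal 5% test, B versus C, by formula**

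| CV | k | Shared SE (mg) | SD 0.9 mg | SD 1.2 mg | SD 2.0 mg |
|---|---|---|---|---|---|
| 1% | 20 | 0.033 | 5.4% | 5.2% | 5.1% |
| 2% | 50 | 0.042 | 5.6% | 5.3% | 5.1% |
| 2% | 10 | 0.094 | 8.1% | 6.7% | 5.6% |
| 3% | 5 | 0.199 | 18.4% | 12.8% | 7.8% |
| 5% | 5 | 0.332 | 34.3% | 24.5% | 12.8% |

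**Simulation of the signed-rank test itself.** At SD 0.9 mg it gave 7-8% (CV 2%, 10 pouches), 17-18% (3%, 5) and 31-33% (5%, 5). With no reference error it gave 4.8%, so the excess comes from the shared term alone. The formula runs slightly high.

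**Simulation that generates pouch content, weight, residual and reference pouches**, with equal true extraction for B and C. Here the variation in pouch content also widens the differences (SD about 1.0 mg at CV 5%). At CV 5% the planned test gave:

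| k | 3 | 5 | 10 | 20 | 50 | 200 |
|---|---|---|---|---|---|---|
| Type I error | 34.3% | 27.3% | 17.9% | 11.1% | 7.1% | 5.2% |

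A separate simulation of the same kind gave 6.7% (CV 2%, 10), 13% (3%, 5) and 24.5% (5%, 5).

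**Other pairs.** For A versus B at CV 5%, k = 10 and SD 1.0 mg, the simulated signed-rank test gave 12.2%, against 17.7% for B versus C.

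**The case against.** **The size rests on assumptions.** This stands. With many reference pouches, a low CV or widely spread differences, the inflation is close to nil. Nothing in the protocol shows which case applies.

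**A reader might infer that up to half of null comparisons would come out significant.** The formula does return 49.8% for CV 5%, 5 pouches and SD 0.6 mg, but the documents do not support that combination. If pouches differ by 5% in concentration, the used pouches do too. That alone puts 0.05 × 14.86 = 0.74 mg into the SD of differences if the milligrams extracted do not depend on content (less if extraction is proportional to content). An SD of 0.6 mg would then be impossible, and even an SD of 0.74 mg gives about 42%. Pairing a high CV with few pouches also stacks two adverse assumptions.

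**A reader might infer that a larger trial would give a worse answer.** The shared error does not grow with the number of subjects, and the estimate's total error still falls. Only the test's false-positive rate rises, because its own standard error shrinks while the shared error stays put. The sample is fixed at 24 in any case, and fewer may contribute, since a positive SARS-CoV-2 test on Day 5 removes a subject from this analysis (section 11.4.7).

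**This is detail for the SAP.** Section 17 does defer technical detail, and the SAP, which is not shown, may add an interval or rest on ample reference pouches. But the protocol itself fixes both the formula and the test, and an analysis that follows them as written carries the problem.

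**Little depends on it.** Section 7.2 frames the endpoint as serving the correlation with AUC, and no decision rule is attached. Assay calibration error common to reference and used pouches may also partly cancel. Both points limit the consequence. Neither removes the sampling error of the reference mean.

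**Conclusion.** The point holds as a minor one. Section 17.6.2 prescribes a test that omits a source of error built into its own formula. Assuming no true difference between B and C, 24 pairs and a nominal 5% level, the true type I error is about 5-6% with CV 1-2% and 20-50 reference pouches, or with SD about 2 mg, CV 2% and 10 pouches. It rises to about 13-30% with CV 3-5%, 5 pouches and SD about 0.9-1.2 mg. In the worst of these settings the formula gives 34%, while simulations that generate pouch content give 24.5-27.3%. Material inflation is therefore possible but not shown. The documents do not support reading this as a defect in the primary analysis: C_max and AUC_t do not use the reference pouches.

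**What to change.** Alongside or in place of the bare test, report the estimated product difference in extracted dose with a 95% CI that includes the reference error. Either of two routes will do:

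- **Resampling:** bootstrap subjects and reference pouches together, recomputing each product's mean concentration in every resample.
- **Variance formula:** variance of the mean difference = SD²/n + the sum over the two products of (mean pouch weight)² × (reference concentration variance / number of reference pouches).

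The second route, with Satterthwaite degrees of freedom, held type I error at 4.5-5.7% in every setting of the simulation that generated pouch content (CV 2%, 5% and 10%; 3 to 200 reference pouches). The planned test ranged from 5.2% to 44.9% over the same settings, the top value coming from CV 10% with 3 pouches. State the number of reference pouches per product next to the result.

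The cost is a few lines of analysis wording, a short computation and somewhat wider intervals. The individual reference-pouch data are already among the inputs in section 17.6.2, so the fix needs no new samples, visits or subject burden.

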Baseline symptoms ⁵	11.2.12	X	X	X					
Adverse events ⁶	11.4.6				----- X -----				
Prior and concomitant medications	11.2.7				----- X -----				

BMI = Body mass index, WOCBP = women of childbearing potential, HIV = human immunodeficiency virus

1. Confirmation of eligibility criteria on Day-1 or Day 1

2. WOCBP only. Urine dipstick.

3. Clinical laboratory panel to include testing for SARS-CoV-2 (qPCR testing) on Day 5.

4. Meals (breakfast, lunch, snack, dinner and evening snack) will be served at the research clinic during Visit 2. On Day 1-5, lunch, snack, dinner and evening snack will be served approximately 4, 7, 9 and 11 hours, respectively, after start of each IP use. Breakfast will be served approximately 1 hour before start of each IP use.

5. Baseline symptoms will be recorded up until start of first use of IP on Day 1.

6. Adverse event will be recorded from start of first use of IP on Day 1.

Table 8.1-2 Detailed schedule of events for Day 1, Day 2, Day 3, Day 4 and Day 5

Assessment /time-point	Pre-IP use	Day 1, Day 2, Day 3, Day 4 and Day 5														
		00:00	00:02	00:05	00:07	00:15	00:20	00:30	00:45	01:00	01:30	02:00	04:00	06:00	08:00	12:00
Inclusion/exclusion criteria	X ¹															
Vital signs (Blood pressure and pulse)	X														X	
12-lead ECG															X ²	
Clinical laboratory profile															X ²	
PES	X ³		X ³		X ³											
MCEQ ⁴															X	
PPS															X ²	
Randomisation	X															
IP use		----- X -----													Ad lib use until 10 pm ⁵	
PK blood sampling ⁶	X	X	X	X	X	X	X	X	X	X	X	X	X	X	X	
Cotinine sampling	X												X		X	X ⁷
Nicotine pouch collection								X								
Meals ⁸		----- X -----														
Baseline symptoms ⁹	X															
Adverse events ¹⁰		----- X -----														
Prior and con meds		----- X -----														

1. Confirmation of eligibility criteria on Day-1 or Day 1.
2. Day 5 only. Clinical laboratory panel to include testing for SARS-CoV-2 on Day 5.
3. PES question 1a-g pre-use only, PES question 2a-j at timepoints 2 minutes to 4 hours, PES question 3a-y at timepoint 8 hours, PES question 4a at timepoints 30 min and 8 hours.
4. Cigarette arm only.
5. The number of units of IP used during *ad lib* use will be reported in the eCRF at the end of each treatment day.
6. PK sampling for 8 hours post-IP use on Days 1-5, respectively. Pre-use sample to be taken within 5 minutes of start of IP-use. PK sampling time windows, refer to Section 11.3.1.

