11.4 Assessments related to secondary endpoints

11.4.1 *Pharmacokinetic sampling and analysis for secondary endpoints*

Refer to Section 11.3.1.

11.4.2 *Nicotine extraction and flavour analysis from pouches*

The individual nicotine pouch given in the morning and the first pouch for *ab lib*-use will be weighed (in grams, with 2 decimals) before administration to the study subjects. The weight of each pouch will be recorded in the eCRF.

Used pouches will be collected after 20 minutes (+/- 1 minute) of use for the determination of residual nicotine in the IPs (morning pouch) and flavour analysis (*ad lib*-pouch). After the 20-minute exposure period, each pouch will be collected into a labelled poly bag, sealed and frozen. The label should have study number, day number, subject ID and product ID.

All the collected pouches will be frozen immediately at -20°C. Pouches for extraction of nicotine and flavour analysis will be analysed by Reemtsma Labs, Hamburg.

11.4.3 *Products evaluation scale*

The subject will self-assess their experience of product effect using the PES at timepoints detailed in Table 8.1-2.

The rating for each question will be done using a 100 mm VAS scale with the anchor points 0 mm (= Not at all/no urge) and 100 mm (= extremely/extreme urge) printed on paper.

The self-assessment for each question at each time point (in mm's) will be entered in the eCRF by the study personnel.

11.4.4 *Modified cigarette evaluation questionnaire*

The subject will self-assess their experience of cigarette product effect using the MCEQ (12 sub-questions) at timepoints detailed in Table 8.1-2. This questionnaire will only be administered after use of the cigarette product.

Each sub-question about how the study product made the subject feel will be assessed on paper on a 7-grade scale (1- not at all, 2- very little, 3-a little, 4-moderately, 5-a lot, 6- quite a lot, 7-extremely).

The score for each sub-question at each time point will be entered in the eCRF by the study personnel.

11.4.5 *Products preference scale*

The subject will self-assess their product preference using the PPS (2 sub-questions) at timepoints detailed in Table 8.1-2.

The sub-questions: "Please rate the 3 pouch products in order of preference." and "Please rate your use of a cigarette vs use of pouch." (1- prefer cigarette, 2- no preference, 3-prefer pouch) will be assessed at the end of Day 5.

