17.1 General

Continuous data will be presented in terms of evaluable and missing observations, arithmetic mean, SD, median, minimum and maximum value. In addition, for the parameters AUC and C_{max} the geometric mean and coefficient of variation (CV) will be presented.

Categorical data will be presented as counts and percentages. When applicable, summary data will be presented by treatment, and by assessment time. Individual subject data will be listed by subject number, treatment, and, where applicable, by assessment time.

All descriptive summaries and statistical analyses will be performed using SAS Version 9.4 or later (SAS Institute, Inc., Cary, NC).

Baseline will be defined as the visit with last data collection point prior to the first use of IP.

No imputation of missing data will be performed.

For subject questionnaires measured at each PK time point, the Bonferroni-Holm p-value adjustment will be applied.

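### The PES total score tested and graphed at each time point repeats the sub-category asked then at 11 of 13 time points, because sub-categories 1, 2 and 3 are never asked together

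*Protocol*

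**What the plan says.** Section 17.6.3 of the protocol plans descriptive statistics for each sub-question, each sub-category and "the total score of Questions 1a-g (sub-category 1), 2a-j (sub-category 2), 3a-y (sub-category 3) and 4a", presented "by product including a graph of the mean at each time point". It then states that "The total score of PES and the sub-categories will be calculated for each product" and that the "intraindividual difference for each timepoint assessed will be analysed using a Wilcoxon Signed Rank Sum test".

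Footnote 3 of Table 8.1-2 fixes when each part is asked: "PES question 1a-g pre-use only, PES question 2a-j at timepoints 2 minutes to 4 hours, PES question 3a-y at timepoint 8 hours", and "PES question 4a at timepoints 30 min and 8 hours".

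Section 11.4.3 has every question rated on a 100 mm visual analogue scale. Section 17.1 adds that, for questionnaires measured at each PK time point, "the Bonferroni-Holm p-value adjustment will be applied". It does not say which tests belong to one family.

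**The concern.** The total in section 17.6.3 spans three sub-categories and item 4a, yet the schedule never collects any two of those sub-categories at the same time point. A total calculated time point by time point is then mostly a second name for the sub-category asked at that moment.

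Three things are at stake. The same Wilcoxon test would be run and reported twice. A graph of the total over time would join scores built from different questions. And testing at every time point includes the pre-use rating, where a product comparison is made before that day's product has been used.

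**Working it through.** The protocol gives no power, alpha or test count for the PES, so there is no stated figure to reproduce. The check is a count.

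**Inputs.** Items per block, from section 17.6.3: 1a-g = 7, 2a-j = 10, 3a-y = 25, 4a = 1. Timing comes from footnote 3 of Table 8.1-2 and the time columns of that table. The item range, 0 to 100 mm, is from section 11.4.3. There are five products (section 8.1).

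**What a total contains at each time point.** The last two columns assume a plain sum, which the protocol does not specify.

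| Time point | Asked | Items | Maximum (mm) | Score if every item is marked 50 mm |
|---|---|---|---|---|
| Pre-use | block 1 | 7 | 700 | 350 |
| 2, 5, 7, 15, 20 min | block 2 | 10 | 1000 | 500 |
| 30 min | block 2 + 4a | 11 | 1100 | 550 |
| 45, 60, 90 min, 2 h, 4 h | block 2 | 10 | 1000 | 500 |
| 8 h | block 3 + 4a | 26 | 2600 | 1300 |

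PES time points: 1 + 5 + 1 + 5 + 1 = 13. Nothing is asked at 6 h.

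**Exact duplication.** The total and the sub-category are the same score at 1 + 5 + 5 = 11 time points, so the Wilcoxon result is identical there, whether the score is a sum or a mean.

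**Near duplication at 30 min and 8 h.** Take items with equal variance and an assumed common inter-item correlation r. The correlation between a k-item sum and the same sum plus one item is

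(V_k + k·r) / √(V_k · V_{k+1}), with V_k = k + k(k−1)r.

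- k = 10, r = 0: 10/√(10 × 11) = 0.953. At r = 0.6: 70/√(64 × 77) = 0.997.
- k = 25, r = 0: 25/√(25 × 26) = 0.981. At r = 0.6: above 0.99.

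**Graph.** As a sum, a subject marking 50 mm throughout would trace 350, 500, 550, 500, 1300 with no change in response. As a mean, the range stays 0 to 100 mm, but the questions behind the curve still change.

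**Multiplicity, assuming alpha 0.05.** Sub-category tests per product pair: 1 + 11 + 1 = 13. Total-score tests: 13. If pooled within a pair there are 26, and the first Holm threshold moves from 0.05/13 = 0.0038 to 0.05/26 = 0.0019. If all 10 pairs of five products are also pooled (an assumption), the count goes from 130 to 260 and the threshold from 0.00038 to 0.00019. If each score has its own family, the total changes no sub-category threshold.

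**Pre-use test.** Block 1 is asked only before use. In the five sequences of section 9.9 each product follows the same predecessor on every day except Day 1, and section 10.6 allows *ad lib* use of that predecessor until 10 pm the evening before. A pre-use comparison labelled with that day's products therefore compares, in large part, mornings after two other products.

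**The case against.** The protocol leaves detailed elaboration to an SAP that is not shown, and section 17.6.3 can be read as a total within each block, or as one score per product day. The test sentence weighs against the within-block reading, since it lists the total beside the sub-categories and tests at each time point. One score per product day would not conflict with the schedule, but it could not be tested or graphed by time point. What section 17.6.3 plans still has to be reconciled with footnote 3.

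Several stronger readings are tempting but not supported:

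- *No parts of the total are ever asked together.* This is true of sub-categories 1, 2 and 3 but not of item 4a, which is asked with block 2 at 30 minutes and with block 3 at 8 hours.
- *The score jumps at 8 hours.* That needs a sum, which is not stated. It also affects only the graph: within a time point all products have the same items, so the between-product tests stay valid.
- *The total inflates the Holm family.* That needs a pooled family, which section 17.1 does not define. Even then, extra tests only make Holm more conservative; they do not create false claims.
- *The total adds items that move in opposite directions.* The anchors, "0 mm (= Not at all/no urge) and 100 mm (= extremely/extreme urge", show that urge and effect ratings share a scale, but the item wording is not shown. Advice to separate or reverse urge items has no basis in the document.
- *The pre-use rating can only reflect the previous product.* On Day 1 no study product precedes it, and in an open-label study expectation may contribute. What stands is that it cannot measure the effect of using that day's product.

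**Conclusion.** The point holds as a conflict between a planned analysis and the protocol's own schedule. Read per time point, the PES total duplicates a sub-category exactly at 11 of 13 time points and differs by one item at the other two, so it adds almost no information and should not be tested or graphed as a separate score. The duplication follows from the documents alone. The change in scale over time depends on a sum score. The doubling from 13 to 26 tests per pair depends on pooling, and the thresholds also depend on an assumed alpha of 0.05. The pre-use comparison is mislabelled as a product comparison under any of these assumptions.

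The consequence is small. The sub-category results are reported anyway, the endpoint is secondary, and the primary analysis of C_max and AUC_t is untouched. This is a worthwhile tidying, not a threat to the trial's conclusions.

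**What to change.** In section 17.6.3, delete the per-time-point PES total from the tests and the graph. Test block 2 at its 11 time points from 2 minutes to 4 hours, block 3 at 8 hours, and item 4a on its own at 30 minutes and 8 hours: 11 + 1 + 2 = 14 tests per product pair. Report block 1 descriptively as pre-use state. State in section 17.1 or the SAP which of these tests form a Holm family; if they are pooled within a pair, the first threshold is 0.05/14 = 0.0036, against 0.0019 with the total and all sub-categories pooled.

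The cost is a wording change in the protocol and SAP. No data collection changes and fewer analyses are run. The downside is that there is no single overall PES number.

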7.2 Secondary objectives and endpoints

Table 7.2-1 Secondary objectives and endpoints

Secondary objectives	Secondary endpoints	Assessment(s)
To evaluate other pharmacokinetic parameters of nicotine after the use of each product	AUC timepoint 0 to 90 minutes (AUC_{0-90}), AUC timepoint 0 to infinity (AUC_{inf}), time to C_{max} (T_{max}), plasma concentration at last timepoint measured (C_{last}), terminal elimination half-life ($T_{1/2}$)	Pharmacokinetic sampling and analysis, (Refer to section 11.3.1)
To evaluate extracted dose of nicotine in used products	The extracted dose of nicotine from each portion to evaluate the correlation between AUC and extracted dose of nicotine.	Collection of pouches and analysis (Refer to section 11.4.2)
To evaluate product perception and preference by use of subjective assessments	Subjective smoking effects	Product evaluation scale questionnaire (PES) (Refer to section 11.4.3) Modified cigarette evaluation questionnaire (MCEQ) (Refer to section 11.4.4) Products preference scale (PPS) (Refer to section 11.4.5)
To evaluate the tolerability and safety of each of the products used	Frequency, intensity and seriousness of adverse events (AEs)	AE reporting and questioning (Refer to section 11.4.6)

	Clinically significant changes in laboratory parameters, vital signs and ECG	Blood sampling for clinical chemistry and hematology (Refer to section 11.4.7) Blood pressure and pulse (Refer to section 11.4.8) 12-lead ECG (Refer to section 11.4.9)
To evaluate the total nicotine exposure by measuring cotinine following single and ad lib use of each of the products.	Assessment of total nicotine exposure following plasma cotinine levels (concentration and applicable calculated PK parameters) following controlled single use and ad lib use of IP	Blood sampling for analysis of cotinine (Refer to section 11.4.10)

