9.9 Randomisation

On Day 1, subjects will be randomised to one of 5 treatment sequences. The five different products are:

- A: ZoneX #2, OND, white tobacco-free nicotine pouch, 5.8 mg nicotine/pouch
- B: ZoneX #3, OND, white tobacco-free nicotine pouch, 10.1 mg nicotine/pouch
- C: Skruf snus fresh slim white, 10.9 mg nicotine/pouch
- D: [REDACTED]
- E: Marlboro Gold, conventional cigarette, 0.8 mg nicotine/cigarette

The 5 randomisation sequences are:

Sequence 1: A:B:C:D:E

Sequence 2: B:C:D:E:A

Sequence 3: C:D:E:A:B

Sequence 4: D:E:A:B:C

Sequence 5: E:A:B:C:D

A computer-generated randomisation list will be created by CTC using SAS Proc Plan, SAS Version 9.4. The randomisation list will contain subject number, sequence and treatment and will be kept by the randomiser until database lock. A copy of the randomisation list will be provided to the research clinic.

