11.4.6.10 Recording adverse events

AEs must be recorded in the AE Log of the eCRF. The Investigator must provide information on the AE, preferably with a diagnosis or at least with signs and symptoms; start and stop dates, start and stop time; intensity; causal relationship to IP; action taken, and outcome.

If the AE is serious, this must be indicated in the eCRF.

AEs, including out-of-range clinically significant clinical safety laboratory values, must be recorded individually, except when considered manifestations of the same medical condition or disease state; in such cases, they must be recorded under a single diagnosis.

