17.5 Analysis of primary endpoints

17.5.1 *Analysis of pharmacokinetics*

The PK analysis will be based on the PK analysis set and performed by CTC. The PK parameters will be calculated by non-compartmental analysis (NCA) using the software Phoenix WinNonlin® version 8.1 or later (Certara, U.S.A.).

The following non-compartmental PK parameters will be determined for each IP use:

- AUC_{inf} (baseline adjusted [when possible] and non-baseline adjusted)
- AUC_t (baseline adjusted [when possible] and non-baseline adjusted)
- AUC_{0-90} (baseline adjusted [when possible] and non-baseline adjusted)
- C_{max} (baseline adjusted [when possible] and non-baseline adjusted)
- C_{last} (baseline adjusted [when possible] and non-baseline adjusted)
- T_{max} (baseline adjusted [when possible] and non-baseline adjusted)

- $T_{1/2}$ (baseline adjusted [when possible] and non-baseline adjusted)

$\text{Lambda}_{\text{az}}$ (with acceptance criteria; R^2 , extrapolated AUC) will be calculated to support baseline adjustment of above PK parameters.

C_{max} and T_{max} will be derived from the observed plasma concentration data. The AUC will be calculated using log-linear trapezoidal interpolation (linear - up, log - down). Calculations will be based on the actual sampling times recorded during the study. Concentrations below Lower limit of quantification (LLOQ) occurring before C_{max} will be treated as zero.

Concentrations below LLOQ occurring after C_{max} will be omitted from the analysis. AUC_t , and C_{max} will be corrected for and calculated with and without nicotine baseline corrections. Where plasma nicotine concentrations are above the lower limit of quantification immediately prior to product use (-5 minutes), PK parameters will be calculated from baseline adjusted concentrations using subjects' elimination rate constant.

Summary statistics for the PK parameters will be presented by product with number of measurements, arithmetic mean, SD, CV, median, minimum, maximum, geometric mean, geometric CV%. All data will be listed by subject.

The primary objective will be examined by the following statistical comparisons for AUC_t and C_{max} :

- Product A versus Product B, C, D and E, respectively
- Product B versus Product C, D and E, respectively
- Product C versus Product D and E, respectively
- Product D versus Product E

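### Adverse events and vital signs are to be tabulated by sequence, although the objective is the safety of each product and every sequence contains all five products

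*Protocol*

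**What the plan says.** Protocol 7.2 gives the safety objective as "To evaluate the tolerability and safety of each of the products used". Two endpoint sections then fix how the safety data are summarised:

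- 17.6.6, adverse events: "Incidence of AEs and SAEs will be summarised by SOC and PT by sequence and overall". The separate overview table in that section is organised by SOC and PT and names no product.
- 17.6.8, vital signs: "Vital signs (systolic/diastolic blood pressure and pulse) will be summarised by sequence".

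On the design, 9.9 says "On Day 1, subjects will be randomised to one of 5 treatment sequences" and lists them: ABCDE, BCDEA, CDEAB, DEABC and EABCD.

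Elsewhere the analysis sections name product as the grouping. For pharmacokinetics, 17.5.1 says "Summary statistics for the PK parameters will be presented by product with number of measurements". For the product evaluation scale, 17.6.3 says that results "will be presented using descriptive statistics at selected timepoints by product including a graph of the mean at each time point".

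Section 17.1 adds a general rule that summaries are given by treatment when applicable, and on listings it says: "Individual subject data will be listed by subject number, treatment, and, where applicable, by assessment time".

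**The concern.** In a crossover where every subject is due to use every product, sequence describes only the order of use. A table of adverse events by sequence therefore compares five groups that have all used A, B, C, D and E. It cannot show whether one product is tolerated worse than another, which is what the objective asks.

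Vital signs are slightly different, because they are taken before use and at 8 hours on each of Days 1 to 5 (Table 8.1-2). A sequence-by-day layout would hold one product per cell. Each product would still be spread over five small cells, with no summary over all its users.

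At stake is whether the planned summaries answer a stated secondary objective. Section 6.1.2 describes this as the first clinical study of the ZoneX products, and 8.2 expects its safety data to support later studies. The primary pharmacokinetic analysis is not affected.

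**Working it through.** The plan states no figure to reproduce: 17.2 says that no formal sample size calculation was done, and no event rate or blood pressure SD is given. The check has a structural part, which needs no assumptions about rates, and an illustration, which does.

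**Inputs from the protocol.** 24 subjects (9.3); five sequences (9.9); one product per day on Days 1 to 5; vital signs before use and at 8 hours each day (Table 8.1-2).

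**Structure.** Each of the five sequences contains the set {A, B, C, D, E} once. Each day also contains each product once across the five sequences. With allocation as even as possible (assumed), 24/5 = 4.8, so 4 or 5 subjects per sequence. A product column would rest on up to 24 subjects.

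**Adverse events.** Let p be the chance of any adverse event on a given product, with days independent and no carry-over or order effect (assumed). For any sequence:

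P(any event) = 1 − (1−pA)(1−pB)(1−pC)(1−pD)(1−pE)

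This product does not depend on the order of its terms, so every sequence has the same expected incidence whatever the five risks are. With assumed risks:

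| Assumed risks A / B / C, D, E | Each sequence column | By product, A against B |
|---|---|---|
| 5% / 15% / 10% | 1 − 0.95×0.85×0.9³ = 41% | 10 points apart |
| 10% / 30% / 20% | 1 − 0.9×0.7×0.8³ = 68% | 20 points apart |
| 20% / 60% / 40% | 1 − 0.8×0.4×0.6³ = 93% | 40 points apart |

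In the middle row, the by-product table expects 24×0.10 = 2.4 subjects on A and 24×0.30 = 7.2 on B. The expected difference between sequence columns is 0 in every row.

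Observed columns would still differ by chance. At 67.7%, the SD of one column's proportion is √(0.677×0.323/n), which is 0.234 for n = 4 and 0.209 for n = 5, or 21 to 23 percentage points. A reader could mistake such differences for a signal.

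**Vital signs.** The standard error of a mean change is SD/√n. With an assumed SD of 8 to 12 mmHg:

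| SD (mmHg) | n = 4 | n = 5 | n = 24 |
|---|---|---|---|
| 8 | 4.0 | 3.6 | 1.6 |
| 12 | 6.0 | 5.4 | 2.4 |

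The ratio does not depend on the SD: √(24/5) = 2.19 and √(24/4) = 2.45.

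**Feasibility.** Section 11.4.6.10 requires "start and stop dates, start and stop time; intensity; causal relationship to IP" for each event, so an event can be placed in the period of one product. The vital-sign schedule already gives two readings per product.

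**The case against.** The strongest reply is that 17.1 provides for summaries by treatment when applicable. A by-sequence table does not rule out a by-product one, and Section 17 gives only principal features, with detail to follow in the SAP. The phrase may also be template wording, since it recurs for demographics, concomitant medication, the smoking index and ECG. Listings carry treatment, so nothing is lost. The illustrative rates and SDs are not the trial's own.

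Part of this stands. A by-product summary can be rebuilt from the listings, and the SAP could add one. Whether the wording was deliberate does not matter to the conclusion. The numbers are illustrations, but neither the equality of the sequence columns nor the standard error ratio depends on them. For vital signs, the loss is the pooled product summary; the individual cells can still be identified.

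The rest does not hold. The endpoint sections do not leave the grouping open: they name one, and it conflicts with the objective. The 17.1 rule is conditional and does not replace the specific instruction. Where the protocol means to defer to the SAP, it says so, as in 17.6.10 for cotinine.

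Exposure on Day 5 also differs: there is no ad lib use, and follow-up runs to the telephone call on Day 7 (±1). This complicates assigning events to products, but each product falls on Day 5 in exactly one sequence, so the difference is spread about equally over the products.

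**Conclusion.** The concern holds. As written, the adverse event incidence table cannot show differences between products, because every column pools all five. The vital-sign summary splits each product into cells of 4 or 5, with standard errors 2.2 to 2.4 times those of a 24-subject summary. The equality of expected sequence columns rests on independent days and no order or carry-over effect, and on no particular rates. The percentages quoted rest on assumed risks, and the cell sizes on near-even allocation with all subjects completing.

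This should be fixed. It is a wrong grouping for a descriptive secondary objective. Data collection and the primary analysis are untouched, and the listings allow recovery by hand.

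**What to change.** - **17.6.6:** make product, plus overall, the grouping for AE and SAE incidence by SOC and PT. Add an attribution rule: an event belongs to the product in use at onset, from that product's first use until the first use of the next product. Events after the Day 5 use belong to the Day 5 product.
- **Onset times:** confirm that start time is captured on Days 2 to 5. Section 11.4.6.10 asks for it for every event, but 11.4.6.4 names it only for the day of first use.
- **17.6.8:** summarise vital signs by product and time point, with change from study baseline. Change from the same day's pre-use value can be shown alongside as an option.
- **17.6.7 and 17.6.9:** state that Day 5 laboratory and ECG results follow exposure to all five products and cannot be attributed to one.

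The cost is revised wording and table shells. No new data are needed, and by-sequence tables can be kept as a supplement.
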